3. ANALYSIS SETS

3.1. Full Analysis Set

On the basis of the intent-to-treat (ITT) principle, the Full Analysis Set will include all randomized subjects who use the study products and have baseline and at least one post-baseline efficacy or tolerance data point.

3.2. Per-Protocol Analysis Set

The Per-Protocol Analysis Set will include all subjects completing the study without major protocol deviations. The subjects with major protocol deviations will be determined before unblinding.

A secondary analysis based on the per-protocol analysis set will be performed on the primary efficacy endpoint.

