3. OVERALL STUDY DESIGN AND PLAN DESCRIPTION

This is a multi-center, 2-cell, full-face, randomized, evaluator-blind clinical usage study. Up to 136 subjects will be enrolled to finish with at least 90 subjects (targeting 45 subjects per cell). The target population is 12- to 40-year-old males and females of any skin type who have mild to moderate acne vulgaris on the face. Up to 50% of the enrolled subjects may be male.

Subjects will be randomly assigned to use one of the two acne treatment regimens at home for 12 weeks. Each subject will be instructed to wash his/her face twice daily (morning and evening) with the AM & PM Cleanser. In the evening after washing, subjects assigned to Regimen 1 will use the PM Mask Treatment for 10 minutes, while subjects assigned to Regimen 2 will apply the PM Gel-Cream full-face and let it dry prior to using the PM Mask Treatment for 10 minutes (mask treatment should begin within 15 minutes after PM Gel-Cream application).

Subjects will be assessed at Baseline (Week 0), within 20 minutes after the first product usage, Week 1, Week 2, Week 4, Week 8, and Week 12, according to the Schedule of Events in Table 1 below.

Protocol Title: A Multi-Center, Evaluator Blinded, Randomized Clinical Study to Evaluate the Efficacy and Tolerance of Two Acne Treatment Regimens on Subjects with Mild to Moderate Acne Vulgaris

Protocol Number: PS-1701 0314 5529-SACT

Date & Version: 06 March 2017, Final Version 1.0

Table 1. Schedule of Events

Time Points/Procedures	Visit 1		Visit 2	Visit 3	Visit 4	Visit 5	Visit 6
	Screening/ Baseline (Week 0)	Post-1 st Product Usage ^a	Week 1 (± 1 day)	Week 2 (± 3 days)	Week 4 (± 3 days)	Week 8 (± 3 days)	Week 12 (± 3 days)
Informed consent (and assent, as applicable) with HIPAA disclosure & photograph release	X						
Collect demographics (including Fitzpatrick Skin Type & skin sensitivity), general medical history, & concomitant medications	X						
Interview for compliance			X	X	X	X	X
15-minute acclimation	X		X	X	X	X	X
Acne lesion counts	X ^b			X	X	X	X
Investigator Global Acne (IGA) assessment	X ^b		X	X	X	X	X
Review of eligibility	X						
Subject qualification by medically qualified staff	X						
Enrollment & randomization	X						
Additional investigator efficacy assessments	X		X	X	X	X	X
	■		■	■	■	■	■
	■	■	■	■		■	■
	■	■	■	■	■	■	■
	■		■	■	■	■	■
	■						■
(Pre-weighed, as applicable) IP dispensed with subject instructions and daily diary ^c	X Starter Kit				X Replacement kit	X Replacement kit	

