6.7. APPLICATION/USE OF THE IPs & SUBJECT COMPLIANCE

Subjects will be randomly assigned to use one of the two treatment regimens for 12 weeks (see sections 6.1 and 6.5). As described in section 6.2, they will receive a starter kit of the assigned regimen at Visit 1, and a replacement kit will be dispensed at Visit 4 and Visit 5.

The regimen-specific instructions (Appendix VI or VII) and subject-directed device package inserts (Appendix VIII, IX, and/or X) will be included in the corresponding subject kits.

Regimen/Cell 1: Each subject will be instructed to wash his/her face twice daily (morning and evening) with the AM & PM Cleanser. In the evening after washing, subjects will use the PM Mask Treatment for 10 minutes. See the detailed subject instructions in Appendix VI.

Regimen/Cell 2: Each subject will be instructed to wash his/her face twice daily (morning and evening) with the AM & PM Cleanser. In the evening after washing, subjects will apply the PM Gel-Cream full-face and let it dry prior to using the PM Mask Treatment for 10 minutes (mask treatment should begin within 15 minutes after PM Gel-Cream application). See the detailed subject instructions in Appendix VII.

IP weights/review, daily diary, and subject interview will be used to assess subject compliance. All units of the PM Gel-Cream should be weighed (with weight recorded) prior to dispensing and at each subsequent visit through collection. The AM & PM Cleanser will not be weighed but should be visually assessed for usage compliance. Each Activator supplied to the subjects (as part of the starter or replacement kits) should be reviewed by study staff for usage compliance [REDACTED]
[REDACTED]
[REDACTED]

The diary and Activator must indicate at least 90% compliance (i.e. 3 usage misses in 30 days is allowed); anything less than that will be documented as a compliance deviation and the subject will be re-instructed on proper product usage or be dropped from the study at the PI's or designee's discretion after consultation with the Sponsor.

Subjects are expected to use at least 5 grams of the PM Gel-Cream per week; anything less than that will be documented as a compliance deviation. Subjects should be re-instructed on proper product usage or dropped from the study at the PI's or designee's discretion after consultation with the Sponsor.

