6.3. Statistical Methods

6.3.1. Method for Primary Efficacy Endpoint

The mean percent change from baseline in global face total lesion count at Week 12 within the mask with topical gel-cream treatment cell and the mask alone treatment cell will each be tested using a one-sample t-test.

If both of the above comparisons are significant, the non-inferiority of the mask with topical gel-cream treatment to the mask alone treatment will be evaluated; otherwise, this comparison will be exploratory. Treatment means and between-treatment differences will be assessed by means of an ANCOVA model with treatment, gender, and center as factors and the corresponding baseline score as a covariate. The difference between treatment groups will be computed as the mask with topical gel-cream minus the mask alone treatment, and non-inferiority will be concluded if the upper bound of the two-side 95% confidence interval is less than 15 percentage points.

If the mask with topical gel-cream treatment is demonstrated to be non-inferior to the mask alone treatment, the superiority of the mask with topical gel-cream treatment versus the mask alone treatment will be evaluated. Superiority will be concluded if the upper bound of the two-sided 95% confidence interval of the treatment difference is less than 0.

Impact of center on treatment effect will be assessed in a separate analysis by including the center-by-treatment interaction in the ANCOVA model above. Summary statistics will be presented by treatment and center with no statistical comparison between treatments within a center.

If the global face total lesion count is missing at Week 12 for more than 5% of the subjects, the missing value will be imputed by using the last observation carried forward (LOCF) method. In addition, a sensitivity analysis will be performed using a repeated measure mixed model based on the observed data. The model will include the baseline score as the covariate and terms for treatment, gender, center, visit, baseline-by-visit, and treatment-by-visit interactions. The covariance matrix will be assumed unstructured.

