6.4.2. Efficacy Analyses

All efficacy analyses will be based on the Full Analysis Set which will be the primary analysis. As a secondary analysis, the primary efficacy endpoint will be analyzed based on the Per-Protocol Analysis Set.

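### Does the per-protocol check on non-inferiority need a written definition of major deviations, given that gel-cream weight deviations can arise only in Cell 2?

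*SAP*

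**What the plan says.** SAP 3.2 defines the set in one sentence, "The Per-Protocol Analysis Set will include all subjects completing the study without major protocol deviations", and its timing in the next, "The subjects with major protocol deviations will be determined before unblinding". Neither document lists the major deviations, or says who decides or from which data.

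SAP 6.4.2 ranks the sets: "All efficacy analyses will be based on the Full Analysis Set which will be the primary analysis". The PP analysis repeats the primary endpoint as a secondary analysis. The decision rule in SAP 6.3.1 is that "non-inferiority will be concluded if the upper bound of the two-side 95% confidence interval is less than 15 percentage points". SAP 6.1 to 6.3.1 do not mention the PP set.

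Protocol 6.7 has two numeric compliance rules. One covers both cells: "The diary and Activator must indicate at least 90% compliance (i.e. 3 usage misses in 30 days is allowed". The other concerns the gel-cream alone: "All units of the PM Gel-Cream should be weighed (with weight recorded) prior to dispensing and at each subsequent visit through collection". A shortfall by weight is classed as a deviation in compliance: "Subjects are expected to use at least 5 grams of the PM Gel-Cream per week; anything less than that will be documented". Only one cell has that product; Protocol 3 describes mask use alone for Regimen 1, "while subjects assigned to Regimen 2 will apply the PM Gel-Cream full-face". Under either rule a subject may be re-instructed or, at the investigator's discretion after consulting the sponsor, dropped.

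**The concern.** In a non-inferiority trial, subjects who do not use the product that differs between arms can pull the arms together. A PP analysis is the usual second look. Here its protection is that deviations are fixed before unblinding, yet a gel-cream weight entry identifies Cell 2 to anyone who reads the deviation log.

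The plan does not say whether such an entry is major. If it is, it can remove subjects from one arm only, with the arm known. If it is not, subjects whose non-use shows only in the weights stay in, and the PP set says less about use of the gel-cream. Nor does the SAP say how to report a trial in which the FAS meets the margin and the PP set does not. At stake is whether a reader could rely on the PP result as support for a non-inferiority claim.

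**Working it through.** **1. The plan's own figure.** Inputs from Protocol 8.4: 45 completers per cell, SD 30, margin 15, gel-cream better by 5, one-sided 0.025.

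- Standard error: 30 × √(2/45) = 6.32.
- Distance to the margin: 15 + 5 = 20, and 20/6.32 = 3.16. Noncentral t with 88 df gives 87.9%, against 87% stated.
- With equal regimens: 15/6.32 = 2.37, giving 65.0%.

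Membership of the PP set is not an input to any of these.

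**2. How often could the FAS pass and the PP set fail?** Take the enrolment ceiling and completion floor as 136/2 = 68 per arm in the FAS and 90/2 = 45 in the PP set, with the PP set a random subset. Simulation gives 9.6% at a 5-point benefit and 19.6% at equality. With 50 and 45 per arm it is 4.2% and 7.3%.

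These figures do not measure the concern, because random subsets contain no selection and no knowledge of cell. At equality the pass rates are 82.5% with 68 per arm and 65.0% with 45. That 17.5-point gap is sample size. The remaining 19.6 − 17.5 = 2.1 points equal the share of trials that disagree the other way. A perfectly defined and perfectly blind PP set would show the same rates.

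**3. If weight deviations are called major.** Assume 4, 9 or 14 of 45 Cell 2 subjects are excluded and under-use correlates 0.3 with response; the documents give neither figure. With excluded fraction f and z_f the normal quantile of f, the Cell 2 mean shifts by about 0.3 × 30 × φ(z_f)/(1 − f). For f = 0.089, 0.200 and 0.311 this is 1.6, 3.1 and 4.6 points; simulation gave about 1.5, 3.1 and 4.5. PP pass rates when the regimens are equal (65.0% with nobody excluded):

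| Excluded | Unrelated to response | Poor responders | Good responders |
|---|---|---|---|
| 4 | 62.5% | 71.7% | 54.2% |
| 9 | 60.0% | 76.8% | 42.5% |
| 14 | 56.2% | 79.2% | 32.0% |

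Part of each fall is lost subjects. For 14 good responders, 65.0 − 56.2 = 8.8 points come from size and 56.2 − 32.0 = 24.2 from the shift. At a true 15-point disadvantage the PP set passes in 4.2/6.8/9.5% (poor responders), 1.4/0.8/0.5% (good) or about 2.5% (unrelated).

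A second set of assumptions, with 5 to 20% of Cell 2 excluded and responding 10 to 30 points worse than those kept, shifts the difference by 0.05 × 10 = 0.5 up to 0.20 × 30 = 6 points. The pass rate at the margin is then 3.0 to 14.1%.

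**4. If they are not called major.** Suppose the gel-cream regimen is 15 points worse when used, and a fraction q skips the gel-cream but keeps the mask. The difference becomes 15 × (1 − q). For q = 10, 20 and 30% the pass rate rises from 2.5% to 4.2, 6.8 and 10.5%.

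If these subjects skip the mask too, with an assumed mask-alone mean of −40 and a non-user mean of 0, the difference is 15 × (1 − q) + 40q = 17.5, 20 and 22.5. The rate then falls to 0.9, 0.3 and 0.1%. Either result holds in any set of 45 per arm that keeps such subjects, the FAS included, so it describes non-adherence rather than SAP 3.2.

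**5. Would different wording remove the asymmetry?** Suppose weight were barred from defining the PP set. Protocol 6.7 still lets low gel-cream use lead to a subject being dropped. A dropped subject does not complete and so leaves the PP set anyway, and this too happens only in Cell 2.

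**The case for a change.** The strongest case is this. The stated blind in Protocol 6.6 covers the investigator and evaluators only. By Protocol 6.5 and 8, the sponsor department that devises the randomization scheme also manages and analyses the data. Nothing bars those who classify deviations from seeing lesion counts. The criteria are open, one of them reveals the cell, and a few sentences written before data review would cost little.

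The facts stand, and so does the inference that timing alone would not make a weight-based exclusion blind. Three things limit what follows. First, the SAP does commit to settling the list of subjects before unblinding, and Protocol 6.7 labels low weight a compliance deviation without calling it major, so the route is possible rather than planned. Second, with the FAS named as primary, a disagreement is already ranked: the FAS decides, and a report showing both estimates and intervals lets the reader see the rest. Third, keeping weight out leaves known under-users in a set meant to reflect use as directed, while letting it in thins one arm. That is a trade-off without a clean answer.

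The success criteria in Protocol 9 and parts of Protocol 6.7 are also redacted, so silence there cannot be counted against the plan.

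**Conclusion.** No change to the plan follows. Followed as written, it gives a sound non-inferiority test on the FAS at one-sided 2.5% for the effect as assigned, with 87.9% power under the protocol's assumptions. The undefined term affects a secondary analysis only, and statisticians ordinarily settle such criteria at the review before unblinding. The 90% diary and Activator rule is already at hand for both cells, and nothing in the plan prevents recording there whether weight counts or tabulating exclusions by cell.

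The possible movement in the PP result, about 1.5 to 4.5 points in the first set of scenarios and up to 6 in the second, depends on assumed exclusion rates and an assumed link between under-use and response. It also requires that weight deviations be treated as major. It is a reason to read the PP result with care, and it does not affect the primary conclusion.

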3.3. Safety Analysis Set

The Safety Analysis Set will include all randomized subjects who use study products.

4. ENDPOINTS AND COVARIATES

For each efficacy endpoint, summary statistics will be provided by treatment group at each time point. For continuous variables, descriptive summaries will include number of subjects, mean, standard deviation, median, minimum and maximum values. Distributions of categorical variables will be summarized by presenting the number and percent of subjects in each response category.

4.1. Efficacy Endpoints

4.1.1. Primary Efficacy Endpoint

The primary efficacy endpoint is the percent change from baseline in global face total lesion count at Week 12. The total lesion count is the sum of inflammatory lesions (papules and pustules), open comedones, and closed comedones.

4.1.2. Secondary Efficacy Endpoints

The secondary efficacy endpoints are:

[figure not shown]
- a) The percent change from baseline in face total lesion count:
 - Mean across all post-baseline visits (Week 2, Week 4, Week 8, and Week 12)
 - Mean of Week 2 and Week 4
 - Mean of Week 4 and Week 8
 - Mean of Week 8 and Week 12
 - Week 2, Week 4, and Week 8 analyzed separately
- b) Acne lesion counts at Week 2, Week 4, Week 8, and Week 12. Each of the following lesions will be analyzed for the total face:
 - Open comedones
 - Closed comedones
 - Inflammatory acne lesions (papules and pustules are counted together)
 - Non-inflammatory acne lesions (sum of open comedones and closed comedones)
 - Total lesion counts (sum of inflammatory and non-inflammatory acne lesions counts)
- c) IGA assessment using Modified Cook's Scale at Week 1, Week 2, Week 4, Week 8, and Week 12. Half points may be used:

[figure not shown]
0	Clear	Residual hyperpigmentation and erythema may be present.
---	-------	---

[figure not shown]
1	Almost Clear	A few scattered comedones and a few (less than five) small papules.
2	Mild	Easily recognizable; less than half the face is involved. Many comedones and many papules and pustules.
3	Moderate	More than half of the face is involved. Numerous comedones, papules, and pustules.
4	Severe	Entire face is involved. Covered with comedones, numerous papules and pustules, and few nodules and cysts.
5	Very Severe	Highly inflammatory acne covering the face; with nodules and cysts present.

[figure not shown]
d) Additional investigator efficacy assessments of the following parameters at Week 1, Week 2, Week 4, Week 8, and Week 12:

Parameter	Scale (Half-points may be used)									
	0 = None	1-3 = Mild			4-6 = Moderate			7-9 = Severe		
Overall Redness of Inflammatory Lesions	0 = no redness associated with the inflammatory lesions	1	2	3	4	5	6	7	8	9 = overall, inflammatory lesions exhibit severe degree of redness
Overall Size of Inflammatory Lesions	0 = no longer visible	1	2	3	4	5	6	7	8	9 = overall size is very large

[figure not shown]

[figure not shown]

[figure not shown]

2
P

[figure not shown]

[figure not shown]
Protocol # PS-1701 0314 5529-SACT

[figure not shown]
Statistical Analysis Plan

Protocol # PS-1701 0314 5529-SACT

Statistical Analysis Plan

4.3. Safety Endpoints

Number and percentage of subjects experiencing adverse events.

4.4. Other Endpoints

Not Applicable.

4.5. Covariates

For the primary efficacy variable and secondary efficacy variables, treatment means and between-treatment differences will be assessed by means of an Analysis of Covariance (ANCOVA) model with treatment, gender, and center as factors and the corresponding baseline score as a covariate.

5. HANDLING OF MISSING VALUES

For the analysis of the primary efficacy endpoint, if the global face total lesion count is missing at Week 12 for more than 5% of the subjects, the missing value will be imputed by using the last observation carried forward (LOCF) method.

6. STATISTICAL METHODOLOGY AND STATISTICAL ANALYSES

6.1. Statistical Decision Rules

For the primary efficacy endpoint, the following comparisons will be performed:

1. Mask alone treatment Week 12 vs. baseline
2. Mask with topical gel-cream treatment Week 12 vs. baseline
3. Mask with topical gel-cream treatment vs. mask alone treatment for non-inferiority
4. Mask with topical gel-cream treatment vs. mask alone treatment for superiority

To evaluate the efficacy of the mask alone treatment and the mask with topical gel-cream treatment, statistical comparisons for the primary variable will be based on a stepwise procedure starting with comparisons #1 and #2, which evaluate the monadic efficacy of mask alone treatment and the mask with topical gel-cream treatment, respectively. If both comparisons are significant, testing will proceed to comparison #3 to evaluate the non-inferiority of the mask with topical gel-cream treatment to the mask alone treatment; otherwise, comparison #3 will be exploratory. If the mask with topical gel-cream treatment is demonstrated to be non-inferior to the mask alone treatment, then testing will proceed to comparison #4; otherwise, comparison #4 will be exploratory.

6.2. Statistical Hypotheses

For comparisons #1 and #2, the null hypothesis that there is no difference compared to the baseline will be tested against the alternative hypothesis that there is a difference from the baseline.

Specifically, the following hypothesis will be tested:

$$H_0: \mu_d = 0$$

against the two-sided alternative

$$H_1: \mu_d \neq 0$$

where d is the within-treatment change or percent change from baseline, and μ_d is the mean of the treatment group, i.e., the mask alone treatment or the mask with topical gel-cream treatment.

The mask alone treatment and mask with topical gel-cream treatment each will be considered efficacious monadically if the respective mean percent change from baseline is significantly different from zero at the 0.05 significance level, two-sided.

To compare the mask with topical gel-cream treatment vs. mask alone treatment for non-inferiority (#3), the following hypothesis will be tested:

$$H_0: \mu_A - \mu_B \geq 15\%$$

against the one-sided alternative

$$H_1: \mu_A - \mu_B < 15\%$$

where μ_A and μ_B are the mean percent change at Week 12 of global face total acne lesion count of the mask with topical gel-cream and the mask alone treatment, respectively. The difference between treatment groups will be computed as mask with topical gel-cream minus the mask alone treatment, and non-inferiority will be concluded if the upper bound of the two-side 95% confidence interval is less than 15 percentage points.

For the superiority (#4) test comparing the mask with topical gel-cream treatment vs. the mask alone treatment, with respect to an efficacy variable, the null hypothesis that there is no difference between the two treatments will be tested against the alternative hypothesis that there is a difference.

Specifically, the following hypothesis will be tested:

$$H_0: \mu_A - \mu_B = 0$$

against the two-sided alternative

$$H_1: \mu_A - \mu_B \neq 0$$

where μ_A and μ_B are the means of the mask alone treatment and the mask with topical gel-cream treatment, respectively. Superiority will be concluded if the upper bound of the two-sided 95% confidence interval of the treatment difference is less than 0.

With the stepwise procedure, the familywise error rate will be controlled at the 0.05 level.

6.3. Statistical Methods

6.3.1. Method for Primary Efficacy Endpoint

The mean percent change from baseline in global face total lesion count at Week 12 within the mask with topical gel-cream treatment cell and the mask alone treatment cell will each be tested using a one-sample t-test.

If both of the above comparisons are significant, the non-inferiority of the mask with topical gel-cream treatment to the mask alone treatment will be evaluated; otherwise, this comparison will be exploratory. Treatment means and between-treatment differences will be assessed by means of an ANCOVA model with treatment, gender, and center as factors and the corresponding baseline score as a covariate. The difference between treatment groups will be computed as the mask with topical gel-cream minus the mask alone treatment, and non-inferiority will be concluded if the upper bound of the two-side 95% confidence interval is less than 15 percentage points.

If the mask with topical gel-cream treatment is demonstrated to be non-inferior to the mask alone treatment, the superiority of the mask with topical gel-cream treatment versus the mask alone treatment will be evaluated. Superiority will be concluded if the upper bound of the two-sided 95% confidence interval of the treatment difference is less than 0.

Impact of center on treatment effect will be assessed in a separate analysis by including the center-by-treatment interaction in the ANCOVA model above. Summary statistics will be presented by treatment and center with no statistical comparison between treatments within a center.

If the global face total lesion count is missing at Week 12 for more than 5% of the subjects, the missing value will be imputed by using the last observation carried forward (LOCF) method. In addition, a sensitivity analysis will be performed using a repeated measure mixed model based on the observed data. The model will include the baseline score as the covariate and terms for treatment, gender, center, visit, baseline-by-visit, and treatment-by-visit interactions. The covariance matrix will be assumed unstructured.

